36 readmissions in patients with cirrhosis and their caregivers compared to standard of care.**

37  
38 As part of this specific aim, we will include 450 total cirrhotic patients and 450 caregivers (150 patients and 150 caregivers per center), who will  
39 be followed for 30 days post-discharge. The groups will be randomized 1:1:1 into a standard  
40 of care group, a group receiving health IT interventions who will receive PatientBuddy and EncephalApp Stroop with as-needed follow-up and  
41 another group that receives the same health IT interventions along with scheduled outpatient visits and calls within 30 days of discharge.  
42 Avoidable readmissions will be adjudged using a blinded adjudication committee and the differences between the three groups will be compared.  
43

44 The Health IT groups will be given iPhones loaded with the Patient Buddy app with caregiver and patient interfaces. They will be instructed  
45 extensively regarding the use of the App, which is preloaded with variables that associated with readmissions such as medications and  
46 adherence, issues with cognition and orientation and new symptoms. The patient and the caregiver will have separate devices linked to a device  
47 with the nurse coordinator through which daily communication will occur between patient/caregivers and the study team regarding previously  
48 identified risk factors associated with readmission. With this enhanced communication and educational value of the App, the study team will  
49 have greater access to events at patients' homes and the potential to prevent readmissions by intervening at that stage. The team will also  
50 engage the end-users (patients, caregivers and the nurse coordinator) by inquiring about their input in order to enhance the interface, user-  
51 friendliness and impact of the App. A detailed analysis of 30-day readmissions, including potential preventability with Patient Buddy will be  
52 performed. CITI will be responsible for establishing and monitoring the communication channels and implementation of the interfaces.  
53  
54  
55  
56  
57  
58  
59  
60

1 **Specific aim 2: To incorporate the opinion of key stakeholders (patients, caregivers and nurse coordinators) towards improving the**  
2 **Patient Buddy App in the prevention of readmission in cirrhosis**

3 The input of patients, caregivers and nurse coordinator and analysis of potential preventability of readmissions in specific aim 1 will be used  

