46 the use of the Patient Buddy app is feasible in recently discharged patients with cirrhosis and their caregivers. Eight HE-related readmissions  
47 were potentially avoided after the use of the App. (Note abstract uploaded in documents section) Standard of care follow-up post discharge is  
48 4 weeks (30 days) minimum and possibly 2 weeks depending on the reason for admission, based on the results of our pilot study. Since we  
49 noted poor adherence with the fall -risk assessment and daily sodium intake in the previous pilot version of the Buddy App Study, both have  
50 been removed in the RCT version of this study."

51

52

53

54

55

56

[figure not shown]
57

58

59

60

1  
2 4. \* Describe the proposed research (Figure below is the flow chart for the study design)

**Recruitment of Subjects and Informed Consent Process:** Subjects will be recruited from the Inpatient Service at VAMC. Each morning, the CITI-trained nurse coordinator (who will also act as the nurse coordinator) will check with the inpatient attending if cirrhotic subjects have been admitted. These subjects will be reviewed by the PI and/or co-investigators. If they appear to be reasonable candidates, the coordinator and investigators will discuss the study with them and their caregivers. Sufficient opportunity will be provided to them to have all their questions/concerns answered before consent will be obtained. If subjects and caregivers are agreeable, study activities will start at the day of discharge. All female patients of reproductive age group will undergo a urine pregnancy test.

After informed consent is obtained from both patient and the caregiver separately, we will administer the EncephalApp Stroop to the patient. EncephalApp Stroop is a validated cognitive test that takes 5-10 minutes to perform, which can give valuable information regarding the cognitive flexibility and psychomotor speed of the participant. This has an easier Off State and a more difficult On state. The ultimate outcome is the time taken to complete both Off and On states in seconds known as OffTime+OnTime. The EncephalApp Stroop will be administered by the study team to patients at baseline and at study end in group 1. For those randomized to group 2, it will be administered at baseline to the patient by the study team and then will be taught to the caregiver to administer weekly or if the subject has any issues. Like in group 1, all patients will undergo this again at study end.

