Training will be given to all patients and caregivers regarding

(a) cirrhosis (b) hepatic encephalopathy (c) ascites and low-sodium diet and (d) individual medication evaluation, using printed standardized patient information handouts from UptoDate. We will answer all questions raised by the patients and caregivers and the team will also individualize training based on the specific reason for admission.

We will then proceed with 1:1:1 site-specific randomization in blocks of 4 using a random number generator overseen by the statistician that will be communicated to the sites beforehand.

48

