#### 49 **Group 1: Standard of care group:**

Dyads randomized to the control group will be discharged per local hospital policy with instructions from their team. They will be given the contact number of the study team to call as needed and will then be seen at day 30 of an in-person visit. We will follow the medical record of the patients to evaluate for intervening readmissions but will not call them specifically. The standard of care of these patients is usually either follow-up as needed or occasional phone calls as needed by the clinical team. The standard of care also depends on the acuity of the presentation and the ability of the patient to follow-up. For this study, we will require a 30-day visit from the patient and caregiver.

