 12 readmission. If the patient requires readmission before day 30, their participation will end at that time.

13 **Group 3: Health-IT+Scheduled Follow-up Group:**

14 This group will undergo the training at discharge similar to what was performed in group 2 but we will also intersperse the 30 day follow up with  
 15 one visit and 2 scheduled phone calls as below. Visit Scheduled: Patients and caregivers will be formally called at day 7 and 21 post discharge  
 16 by the study team to inquire about issues that were not communicated via PatientBuddy. We will also perform a study visit at day 15 and day  
 17 30 with both patients and caregivers to define any new changes in the patient's condition, elicit feedback throughout the process and at the day  
 18 visit, returning the devices and resetting them. No additional charges will be generated from the study during these visits.

19 The week 2 visit will include vital signs as well as the discussion of any issues with the buddy app, patient medication update, and any new  
 20 medical issues. The subject will also be given the EncephalApp stroop and orientation test for the week like in group 2. Study staff may also  
 21 observe the caregiver and subject perform their daily app entries. (subject may document medications taken, abdominal girth measurement,  
 22 and daily weight. The caregiver may document medications, daily weight, abdominal girth, orientation questions and stroop test) The study  
 23 staff will offer guidance as needed to complete these tasks. If the patient has a >10lb weight gain from baseline, a >5 inch girth increase, and/  
 24 or is febrile, the study team will notify the hepatologist on service and the PI for direction. No blood will be collected for the study and/or tests  
 25 run for study purposes at any time. However, if the subject is febrile, has overt encephalopathy, is bleeding, and/or is more decompensated,  
 26 the study team will alert the medical team and coordinate care as needed. Any care performed as a result of the findings from this visit will be  
 27 conducted per standard of care by the medical team."

28 FOR GROUPS 2 AND 3: If the subject is re-admitted, they meet the endpoint and their participation will  
 29 end. We will contact the caregiver and coordinate a return of the smartphones and end of study elements. We will also  
 30 request a discharge summary from the outside hospital if they were hospitalized outside of McGuire VAMC. If the patient  

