56 meet with the patient and his/her caregiver at this day 30 visit and will not generate any costs for the pt. We will collect the smartphones and  
57 have the patient and caregiver complete a survey regarding their experience with the app. The pt and caregiver will be together. The questions  
58 to be asked are uploaded to this submission."

59 Decision regarding avoidable readmissions: This will be made by analyzing the discharge summary of the hospitalized patients and will be  
60 classified into avoidable or unavoidable by the committee with three hepatologists (1 each from the 3 sites). The decision regarding avoidability  
is based on the question whether could a clinic visit or earlier communication/education with patient and caregiver prevented this admission.

1 There is no specific hard and fast rule about which admissions are classified as one or the other, which is why a committee is necessary. On  
2 the whole, admissions for elective paracentesis, thoracentesis, early stages of hepatic encephalopathy etc are usually avoidable but those  
3 related to infections, severe hepatic encephalopathy, variceal bleeding etc are usually not considered avoidable. However, since each case is  
4 unique, all discharge summaries of patients admitted within 30 days will be sent to the committee to review and vote. The committee will not be  
told about the assignment of the patients.

5 SAEs: we do not anticipate SAEs i.e. re-admissions to be related to the App itself because that is what is the focus of the study. Therefore,  
6 SAEs simply associated with admissions will not be reported to the IRB. We do not expect other SAEs directly related to the App to appear in  
7 this study.

8  
9  
10  
11  
12  
13  
14 **Active Data Collection**

15  
16. \* **Describe the technology chosen for collecting the data and transmitting data securely over the internet. Give the rationale  
for selecting this technology:**

17 For groups 2 and 3, we will use the Patient buddy app. This has been described in great detail in the uploaded grant but the details are below.  
18 **Patient Privacy and Security:** The App is HIPAA compliant with federal regulations regarding Privacy and Security. Patient Buddy is  
19 considered a Business Associate under the terms of the final HIPAA Omnibus rule. The data management of this study will operate using a  

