**52. \* List the study inclusion criteria:**

53 Cirrhosis patients  $\geq 21$  years of age hospitalized for non-elective reasons

54 • Adult caregiver and the patient living in the same house

55 • Both (caregiver and patient) should be able to complete the Patient Buddy training and evaluation

56 • Discharged home from the hospital

57 •

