## 7 Potential Subject Identification and Recruitment

8

9

10 There will not be any special recruitment flyers since all patients will be hospitalized at VA and will be enrolled through direct contact after  
11 referral or by reviewing the inpatient lists for potentially eligible patients.

12 Subjects will be recruited from the Inpatient Service at VAMC. Each morning, the CITI-trained nurse coordinator (who will also act as the  
13 nurse coordinator) will check with the inpatient attending if cirrhotic subjects have been admitted. These subjects will be reviewed by the PI  
14 and/or co-investigators. If they appear to be reasonable candidates, the coordinator and investigators will discuss the study with them and  
15 their caregivers. Sufficient opportunity will be provided to them to have all their questions/concerns answered before consent will be obtained.

16 If subjects and caregivers are agreeable, study activities will start at the day of discharge

17

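### The plan says the randomisation goes to the sites in advance, the supplied text describes no concealment step, and the stated block of 4 cannot be balanced across three arms

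*Combined protocol and SAP*

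**What the plan says.** The only account of how assignments are generated and delivered is one sentence in item 4 (description of the proposed research), after the paragraph on common training: "1:1:1 site-specific randomization in blocks of 4 using a random number generator overseen by the statistician that will be communicated to the sites beforehand".

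Recruitment is described in the same item and again under Potential Subject Identification and Recruitment. Patients are found through "referral or by reviewing the inpatient lists for potentially eligible patients". Site staff then use judgement: "If they appear to be reasonable candidates, the coordinator and investigators will discuss the study with them and their caregivers".

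The arms cannot be mistaken for one another:

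- Specific Aim 1: "The Health IT groups will be given iPhones loaded with the Patient Buddy app with caregiver and patient interfaces".
- Group 1 (standard of care): "We will follow the medical record of the patients to evaluate for intervening readmissions but will not call them specifically".
- Group 3 (health IT plus scheduled follow-up): "Patients and caregivers will be formally called at day 7 and 21 post discharge", with a study visit at day 15.

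Consent, the baseline EncephalApp and common training come before randomisation. The inclusion criteria apply to every arm: "Both (caregiver and patient) should be able to complete the Patient Buddy training and evaluation". The committee that classifies readmissions is not to be "told about the assignment of the patients".

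Protocol Amendment 2 changes the ratio to 1:1 with 232 patients. It gives no block size and no method of release.

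**The concern.** Randomisation protects the comparison only if the person deciding whether and when to approach a dyad does not know which arm comes next. Here the coordinator and investigators screen, judge and approach. The coordinator and the principal investigator also train the health-IT dyads, so past assignments are plain to the people who recruit. A sentence that sends the randomisation to the sites ahead of time, with no described step that hides the next assignment, leaves that protection unstated at best.

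At stake is the main comparison, avoidable 30-day readmission. If lower-risk dyads could be steered towards one arm, the difference between arms would mix the effect of the intervention with the effect of selection. Baseline comparison and adjustment can deal only with the imbalance that was measured.

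The same sentence also contains an arithmetic error: 4 is not a multiple of 3, so the stated block cannot deliver the stated ratio within a block.

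**Working it through.** The plan states no predictability figure, so there is none to reproduce. The check has two parts.

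**1. What the sentence can mean.** If the list is sent, the next arm is known for 100% of assignments. If only the procedure is sent, staff know the block rule and can see past assignments. A search of the supplied text finds no central, web or telephone release, no sealed envelopes, no release tied to completed enrolment, and nothing on keeping the list or block size from recruiting staff.

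**2. Predictability when only the rule and past assignments are known.** Inputs: block size 4, three arms, stratified by site (item 4); 1:1 after Amendment 2. Assumptions: a fixed block throughout, and an observer who sees every past assignment at the site. For each position in the block, I count the orders in which the next arm is forced, and the chance that the best guess is right, then average over the four positions.

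*Three arms, doubled arm random.* There are 3 × 12 = 36 orders. The fourth assignment is forced when the first three contain a repeat, which is half of the orders.
- Certain: (0 + 0 + 0 + 50)/4 = 12.5%.
- Best guess right: (33.3 + 41.7 + 58.3 + 66.7)/4 = 50.0%, against 33.3% by chance.

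*Three arms, known 2+1+1 composition.* There are 12 orders. The fourth is always forced. The third is forced when the two single arms come first, in 2 of 12 orders.
- Certain: (0 + 0 + 16.7 + 100)/4 = 29.2%.
- Best guess right: (50 + 50 + 58.3 + 100)/4 = 64.6%.

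*1:1, blocks of 4 kept (assumption).* There are 6 orders. The third is forced when the first two match, in 2 of 6 orders; the fourth is always forced.
- Certain: (0 + 0 + 33.3 + 100)/4 = 33.3%.
- Best guess right: (50 + 66.7 + 66.7 + 100)/4 = 70.8%, against 50% by chance.

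**What varied blocks would change.** This was simulated with equally likely sizes and an observer who knows the set of sizes but not the one in use.

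| Scheme | Certain | Best guess right |
|---|---|---|
| Three arms, fixed 4 | 12.5% to 29.2% | 50.0% to 64.6% |
| Three arms, 3/6/9 | 3.8% | 55.3% |
| 1:1, fixed 4 | 33.3% | 70.8% |
| 1:1, 2/4/6 | 4.0% | 70.1% |

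Varied blocks remove most of the certain assignments. They do little for overall guessability, which under three arms lies within the fixed-block range.

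**The case against.** The strongest reply is that the sentence is ambiguous. What is communicated could be the list, the procedure, or each dyad's assignment just before arm-specific training on the day of discharge. The last would be close to the release recommended here. This stands: the text does not settle the meaning, and a reader who infers that the sites were handed the list goes further than the documents do.

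Second, absence is being judged from incomplete text. The flow chart is not shown, some pages were removed, and the form refers to an uploaded grant. This also stands, so the claim is limited to what the supplied text describes.

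Third, there are safeguards. Randomisation follows consent and baseline testing, and ability to use the app is required in every arm. This narrows the room for steering after enrolment, but does not affect whom staff approach or when. The committee's blinding protects classification of the outcome, not allocation.

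Fourth, the figures should not be turned into counts. Applying 12.5% to 150 dyads per site gives 18.75 certain assignments, but that assumes full enrolment under 1:1:1, which Amendment 2 replaced, and one particular block composition. Only the percentages are used here.

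Fifth, concealed release does not cure predictability from past assignments, because those figures already assume an observer without the list. That is correct. Concealed release deals with a site-held list; varied blocks deal with certain assignments; neither removes guessing.

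What does not stand is treating the matter as missing detail only. The plan states an advance communication, and it states a block that cannot be balanced 1:1:1. Both need correction on any reading.

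**Conclusion.** The point holds in a limited form. As written, the plan does not prevent foreknowledge of the next arm. The stated block does not fit three arms, and the scheme for 1:1 is not given.

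How serious this is depends on a fact that the documents leave open. If recruiting staff held the list, it is a serious flaw. If only the procedure was communicated, it is a clarification together with a correction to the block size.

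Under the milder reading, with a fixed block of 4 and visible past assignments, 12.5% to 29.2% of three-arm assignments are certain, and 33.3% under 1:1 if blocks of 4 were kept. A reader might infer that steering took place or that the result is biased by some amount. The documents contain no evidence of steering and no figure from which a size of bias could be derived, so neither is claimed. Confidence is moderate because of the ambiguous wording and the missing flow chart.

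**What to change.** - Delete the clause that has the randomisation sent to the sites in advance. State that the statistician holds the list and that each assignment is released only after consent, eligibility and baseline EncephalApp are recorded, by central release or by sequentially numbered opaque sealed envelopes. This removes foreknowledge from a site-held list.
- Use block sizes that are multiples of the number of arms, varied and not disclosed to the sites, stratified by site (for example 3/6/9 for 1:1:1 and 2/4/6 for 1:1). The expected gain is fewer certain assignments, not much less guessing overall.
- Restate the full scheme, including block sizes, for the 1:1 allocation under Amendment 2.
- For assignments already made, report who held the sequence and when each assignment was released, before and after Amendment 2, and compare baseline characteristics by arm.
- If only the procedure was communicated, say so.

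The cost is a small amount of work to regenerate the lists and run the release step. No extra patients or assessments are needed.

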#### 49 **Group 1: Standard of care group:**

Dyads randomized to the control group will be discharged per local hospital policy with instructions from their team. They will be given the contact number of the study team to call as needed and will then be seen at day 30 of an in-person visit. We will follow the medical record of the patients to evaluate for intervening readmissions but will not call them specifically. The standard of care of these patients is usually either follow-up as needed or occasional phone calls as needed by the clinical team. The standard of care also depends on the acuity of the presentation and the ability of the patient to follow-up. For this study, we will require a 30-day visit from the patient and caregiver.

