#### 54 **Group 2: Health-IT only group:**

Training at the time of discharge: The Patient Buddy app with preloaded caregiver and patient interfaces will be shown to the subjects and caregivers with detailed instructions including: User Guide of Patient Buddy, Quick Reference Sheets for Case Coordinator to give the Patient and Caregiver with screenshots and tips and tricks for maneuvering around the modules, Powerpoint presentation that goes through the workflows for patients and caregivers, and one on one training for the Case Coordinator given by the CITI Representative. In addition, administration of five orientation questions (what is the date, what is the time, what is the year, who am I and where are you?) and EncephalApp Stroop will be taught to the caregiver. The call-in numbers for the nurse coordinator, GI physician on call and the contact information for the

1 principal investigator will also be programmed into the app. A detailed training session will be performed over the next hour by the coordinator  
 2 and the PI to both the patient and the caregiver. This training will be tailored to the specific issues faced by the patient while they were  
 3 hospitalized. The individualized login and passwords for each patient and their caregiver will be established and given to them. A copy will be  
 4 kept with the nurse coordinator in case the subjects forget their codes. These will be reset upon return of the devices at the end of the study.  
 5 The connectivity and messaging system in-built into the Patient Buddy App will then be checked and the control center of the CITI  
 6 communications notified of this enrollment. This will also be checked by sending messages by the patient and caregiver through the App to  
 7 the coordinator and the PI (Figure 3 demonstrates the data flow). In the health-IT only group, there will be daily contacts between patients,  
 8 caregivers and the clinical teams via the App. The only visit scheduled for the study will be at day 30 when the study will be completed.  
 9 However, if there are issues that come up during the intervening period detected via the App, the clinical team will reach out and determine  
 10 with the patients and caregivers if an ad hoc intervening visit is required. The team will not meet with patients or caregivers if they are scheduled  
 11 to be seen as standard of care in their clinics in between the 30 days unless specifically required by the symptoms or if the patient requires  

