 31 is in-house, we will coordinate the end of study while in the hospital if appropriate. The phones distributed to the  
 32 participants in groups 2 and 3 are not capable of making phone calls and have a restricted data plan under CITI. Only  
 33 data entered in the Patient Buddy App will be transmitted directly to the HIPAA-compliant CITI server. At the end of the  
 34 study (at day 30 or readmission within 30 days), the phones will be turned in and remotely wiped of any data. Therefore,  
 35 any other data generated (browsing, photographs etc) performed by the patient/caregiver on their phones will be wiped  
 36 without transmitting over to any other entity. Therefore, there are no privacy or confidentiality risks pertaining to this.

37 Patient Buddy App Use (for groups 2 and 3): The Patient Buddy App will be loaded onto the phones given to the patients and caregivers by the  
 38 study team with the following data and the instructions to get in touch with the team (Table 3)

39 **Contact through Patient Buddy**  
 40 - Daily contacts pertaining to adherence, cognition and measurements as needed (details below)

41 **Unscheduled contacts:**

42 - If nothing is entered in the Patient Buddy for >24 hours by either patient or caregiver  
 43 - Depending on results of scheduled telephone calls  
 44 - Admissions to McGuire VA medical center or after discharge from other hospitals if admitted  
 45 - Telephone calls generated from patients/caregivers to the study team

46 "The study team will reach out to the patient with an open statement such as :"hello \_\_\_\_\_ we noticed you have  
 47 not recorded anything today, is everything ok...any questions? ' The app will be checked by the study team every day. Since the subjects have  
 48 multiple medical problems and their questions are not uniform, the study team will not have a standardized set of responses; they will utilize  
 49 their medical training to address questions appropriately and in the event of progressive decompensation, will alert the medical team and PI and  
 50 coordinate urgent care. Any care performed as a result of the findings from these communications be conducted per standard of care by the  
 51 medical team." Subjects will also be given the number (as is standard of care) for the GI-physician on call and will also be able to call emergency  

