 52 services if they are not able to wait to use Patient Buddy. On the day of discharge, the study coordinator, patient, caregiver and the case  
 53 coordinator will meet for the training and evaluation of the Patient Buddy App as well to check the connectivity.

54 The following data will be collected and reiterated to the patient and the caregiver (Table 3).

55 **Table 3: Patient/Caregiver Logs into the buddy at home daily and to contact study team**

56 Area of interest	57 Specific entry in Patient Buddy	58 To contact study team, GI physician on call or emergency services (marked*)
59 Medication adherence on each medicine on discharge	60 Enter each medicine administration time, date and dose	61 Questions regarding medications, missing or increasing dose
62 New medications and supplements	63 Enter new medicine and dose	64 Call when a new medicine/ supplement is initiated

[figure not shown]
1	Vitals (to be taken at same time every day)	Daily weight	≥3 lb increase in 24 hours
2		Daily Temperature	> 100.4 F or < 96.8 F
3	Cognition (assessed every week or when caregiver feels patient is not acting normally)	Orientation questions (5 questions time/place/person)	Any question abnormal, coma*, confusion, or difficulty waking patient up*
4		EncephalApp Stroop Score	>25 seconds over discharge score(15)
5	Emergency/urgent/other symptoms	Daily bowel movements	<3 or >6 bm/s day (if on lactulose) and any change in those without lactulose
6		GI bleeding (detailed symptoms noted)	Black stools, red blood in stools or vomiting blood*
7		Infections (detailed symptoms noted)	Fever, shortness of breath, burning in urine, abdominal pain, nausea or vomiting
8			
9			
10			
11			

12 The data collected from each patient's medical chart to meet enrollment criteria for this study at discharge will be the  
 13 discharge summary, contact information, and all elements to verify inclusion/exclusion criteria (no  
 14 substance abuse, >21 years of age, non-elective hospitalization, will be discharged home, no dialysis) Also, if the patient is  
 15 re-admitted, discharge summary will again be collected.

16 Training and counseling at the time of discharge: The Patient Buddy app with preloaded caregiver and patient interfaces will be shown to the  
 17 subjects and caregivers with detailed instructions. The call-in numbers for the nurse coordinator, GI physician on call and the contact information  

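### Follow-up of outside-hospital readmissions is written only for the app groups, and no group has an explicit step for detecting them, so capture of the endpoint may be unequal

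*Combined protocol and SAP*

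**What the plan says.** *Group 1.* The section on the standard-of-care group states: "We will follow the medical record of the patients to evaluate for intervening readmissions but will not call them specifically". Dyads receive a study number to call if they wish, and the section adds: "For this study, we will require a 30-day visit from the patient and caregiver". It does not say which records are followed or whether they cover other hospitals.

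*Groups 2 and 3.* After the Group 3 description, a paragraph headed for Groups 2 and 3 deals with readmission. There the team will contact the caregiver and "request a discharge summary from the outside hospital if they were hospitalized outside of McGuire VAMC". Under Patient Buddy App Use, also headed for groups 2 and 3, the list of unscheduled contacts includes "Admissions to McGuire VA medical center or after discharge from other hospitals if admitted". The same list prompts contact when patient or caregiver enters nothing for more than 24 hours. The Group 2 section says: "In the health-IT only group, there will be daily contacts between patients", caregivers and clinical teams. Group 3 adds calls at days 7 and 21 and a visit at day 15.

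*Text that names no arm.*
- After Table 3, a sentence beginning "The data collected from each patient's medical chart to meet enrollment criteria for this study at discharge will be the" lists the enrolment data. The next sentence says that if the patient is "re-admitted, discharge summary will again be collected".
- The section on avoidable readmissions sends the summaries of all patients admitted within 30 days to the adjudication committee.
- The day-30 section, written for all groups, says the study team will "meet with the patient and his/her caregiver at this day 30 visit".
- EncephalApp is given to Group 1 at study end.
- Compensation is paid to dyads who complete 30 days or are hospitalized earlier.

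**The concern.** Specific Aim 1 compares avoidable 30-day readmission between groups, in effect the proportion of patients who have one. Avoidability is judged from the discharge summary, so an admission that is not found, or is found without a summary, cannot be classified. Keeping the assignment from the committee does not help, because unequal case finding would happen before the committee sees anything.

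The protocol expects some admissions to other hospitals, since it provides for them in the app groups. If these are found more often there than in Group 1, the control rate looks lower than it is and part of a real benefit is hidden. The harm comes mainly from the difference in capture between arms; equal loss in both arms costs much less.

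**Working it through.** **1. The written steps side by side**

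| Step | Group 1 | Groups 2 and 3 |
|---|---|---|
| Explicit step to detect an outside admission | None | None |
| Routine contact before day 30 | Medical record; patient may call | Daily app contact; contact after >24 h without entries; Group 3 also calls at days 7 and 21 and a visit at day 15 |
| Contact after an outside admission | Not stated | Stated |
| Request for outside summary | Not stated; arm-neutral sentence only | Stated |
| Day-30 visit | Required | Required |
| Day-30 question on outside admissions | Not stated | Not stated |
| Route if day 30 is missed | Not stated | Not stated |

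The two provisions for Groups 2 and 3 say what to do once an outside admission is known, not how it becomes known. The app groups' likely advantage in detection comes from contact: an outside stay that interrupts entries would itself prompt a call.

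**2. The plan's own figure**

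The sample-size section gives 20% and 9%, 80% power, alpha 0.05 and 45 per group per site (135 per group, 405 in total). The test is not named. A three-group chi-square test with rates 20%, 9% and 9% matches:
- mean rate = (0.20 + 0.09 + 0.09)/3 = 0.1267
- noncentrality = n × [0.0733² + 2 × 0.0367²]/(0.1267 × 0.8733) = 0.0729n
- 80% power on 2 df needs n = 133, or 44.3 per site, rounded up to 45; power at 135 is 80.9%
- 405/0.90 = 450 after 10% dropout

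**3. What control-only loss would do**

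Inputs from the documents: 20% versus 9%, and 232 patients randomized 1:1 (Protocol Amendment 2), taken as 116 per arm. Final arm sizes are not given. Assumed: the share of control events missed, and full capture in the app arm. The documents give neither the share of admissions that go to outside hospitals nor the share that would be missed. A 10% loss is, for example, 20% outside with half of those missed.

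Observed control rate = 20% × (1 − share missed). Power is the exact sum of Bin(x; 116, p₁) × Bin(y; 116, p₂) over all outcomes where the pooled z-test gives |z| ≥ 1.96. Expected control events are 116 × 0.20 = 23.2.

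| Control events missed | Patients | Observed rates | Difference (points) | Power |
|---|---|---|---|---|
| 0% | 0 | 20.0% vs 9% | 11.0 | 67% |
| 2% | 0.5 | 19.6% vs 9% | 10.6 | 64% |
| 5% | 1.2 | 19.0% vs 9% | 10.0 | 60% |
| 10% | 2.3 | 18.0% vs 9% | 9.0 | 52% |

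**4. Other assumptions, same method**
- 10% lost in control and 5% in the app arm (18% vs 8.55%): 57%. 10% lost in both (18% vs 8.1%): 62%.
- Arms of 77 and 155: 65% with full capture; 58% and 50% at 5% and 10% control-only loss.
- The 20% read as a share of the 33% readmitted (33% × 20% = 6.6%; 6.6% × 9/20 = 2.97%), 116 per arm: 24% with full capture; 21% and 18% at 5% and 10% loss.
- No true effect, 20% in both arms, 10% control-only loss: two-sided rejection rises from 5.0% to 6.8%. Of this, 5.8 points would suggest that the app is worse; rejection in the app's favour falls from 2.5% to 1.0%.

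**The case against.** The strongest reply has four parts.

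*Placement.* The paragraph for Groups 2 and 3 is largely about returning and wiping phones, which only those groups have. Its heading does not show that Group 1 was deliberately left out, and the arm-neutral sentences suggest that summaries were meant to be collected everywhere. This stands as to intent. It does not supply a method: the collection sentence follows one about the medical chart, names no source and does not mention other hospitals.

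*Detection in the app groups.* They have no explicit detection step either, and full capture there is assumed. This stands, and the point is worded accordingly. Daily contact is the intervention and cannot be equalized; the day-30 question and the retrieval rule can be.

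*Day 30.* A Group 1 patient whose outside admission went unnoticed is still expected in person with the caregiver, takes the EncephalApp test, holds the study number and is paid even if hospitalized early. This is a real safeguard and makes small losses plausible. It leaves patients who attend but are not asked, and those who miss the visit and do not call. The planned 10% dropout is for the whole trial and shows no difference between arms.

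*Direction.* Control-only loss works against the app, so it would not manufacture a benefit. That is correct, but the effect estimate would still be distorted.

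A reader might infer that Group 1 events were in fact missed, or that the protocol excludes outside admissions in Group 1. The documents support neither: they show unequal written procedures and a silence on method.

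**Conclusion.** The point holds as a risk of unequal capture. Retrieval and contact after an outside admission are written only for Groups 2 and 3. Explicit detection is missing in every group, and contact makes it likelier in the app groups. The safeguards that name no arm reduce the risk without closing it.

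The size cannot be established from the documents. The power figures are illustrations that rest on assumed losses, 116 per arm, 20% read as a share of all patients, and full app-arm capture that no text supports. Given the day-30 encounter, losses toward the lower end of the table or below it are plausible. The 67% starting value reflects the smaller sample under Protocol Amendment 2 and is a separate matter. The change is still worth making, because it protects the main comparison at little cost.

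**What to change.** Write one capture rule for every arm:

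1. At the day-30 visit, ask every patient and caregiver about any admission to any hospital since discharge.
2. If the visit is missed, make the same contact with patient or caregiver in every arm, at or after day 30 so that it adds no contact to Group 1 during follow-up. Report by arm how many remain unknown.
3. Request outside-hospital discharge summaries in every arm and at every site. The present sentence refers only to admissions outside McGuire VAMC, although there are three sites.

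The cost is protocol wording, one question at an existing visit, a contact for those who miss it and a few more record requests in Group 1. Recall at day 30 will be imperfect, but that error should be similar across arms.
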